Noninvasive brain stimulation to evaluate neural plasticity after stroke

Principal Investigator: [name], DPT, PhD

Protocol version 3, dated October 28, 2021

NCT02465034

Research Plan:

This pilot project will recruit a sample of 30 individuals with subcortical stroke aged 18-85 in the chronic phase of recovery with mild-moderate impairment of arm function (Fugl-Meyer upper extremity motor score¹ of less than 61) and 30 healthy controls. In testing sessions at the Neural Plasticity Research Laboratory (NPRL), participants will undergo: 1) noninvasive targeting of cortical locations by stereotactic neuronavigation using TMS, 2) a paired associative stimulation (PAS) protocol using noninvasive stimulation 3) EEG recording during TMS and, 4) arm motor function assessments. Participants may also be asked to complete a single magnetic resonance imaging (MRI) session prior to testing in the NPRL. Up to 5 testing sessions will be performed. The duration of each session will be less than 3 hours.

Inclusion Criteria. Individuals aged 18-85 with a middle cerebral artery stroke will be recruited. Individuals will have a first time stroke that affects the corona radiata and/or internal capsule. Stroke in these regions is common, comprising 34% of the total population². Individuals in the healthy control group will be matched for handedness, gender, age (within 5 years) and education (within 2 years) to each participant in the stroke group.

Exclusion Criteria. Any participant will be excluded if they: 1) are outside the age range of 18-85; 2) show signs of dementia (score < 24 on the Montreal Cognitive Assessment);³ 3) have aphasia (score < 13 on the Frenchay Aphasia Screen);⁴ 4) have a history of head trauma, a major psychiatric diagnosis, neurodegenerative disorder or substance abuse; or 5) report contraindications to TMS.

TMS procedures:

During TMS assessment, stereotactic neuronavigation will be conducted in real-time using the BrainSight system to localize stimulation over the motor representation of the hand bilaterally using a standard brain template (Figure 1). Subjects will be seated comfortably in a reclining

chair during the TMS-EEG assessment. The target muscle for stimulation will be the abductor pollicis brevis (APB). Active motor threshold (% of maximum stimulator output) for the APB representation in M1 will be determined bilaterally using standard protocols⁵. All stimulation parameters fall within published safety guidelines⁶.

Figure 1. Real-time integration of EEG, TMS, EMG and MRI template information using BrainSight system.

Median nerve stimulation

TMS-evoked responses can be modulated when paired with a preceding peripheral nerve stimulus. When peripheral stimulation is applied 20-25ms prior to cortical stimulation, a

reduction in cortical excitability is observed, termed short-afferent inhibition (SAI)^{7,8}. Stimulation of the median nerve will be performed using a bipolar bar electrode affixed to palmar aspect of the forearm proximal to the crease of the wrist bilaterally. Stimuli will be delivered 23ms prior to the TMS pulse with 0.1ms rectangular pulses at an intensity to evoke a 1mV response in the APB.

Paired associative stimulation (PAS) protocols to induce transient shifts in cortical excitability: TMS pulses can be paired with another stimulation pulse at a particular interstimulus interval (ISI) in order to elicit transient changes in synaptic plasticity in humans. For example, long-term potentiation (LTP, a feature of synaptic plasticity) can be measured in humans using a technique termed PAS, which combines TMS and electrical stimulation of the median nerve, to excite the motor cortex (M1).⁸ TMS pulses over M1 can also be combined with TMS pulses delivered over other cortical regions in a 'cortico-cortical' (cc)PAS paradigm to also induce local LTP-like effects.⁹ For each PAS session, individuals will either receive traditional PAS, ccPAS or a sham stimulation intervention. Regardless of PAS group, each participant will receive 180 paired stimuli delivered at 0.25Hz for a total PAS duration of 12min. The ISI will depend on PAS condition. For traditional PAS, median nerve stimuli at 300% of the perceptual threshold will be applied 25ms prior to TMS delivery over the ipsilesional (stroke) or non-dominant (control) cortex. For ccPAS, the interstimulus interval will range from 5-15ms depending on site of stimulation⁹⁻¹¹.

EEG recording of TMS-evoked cortical responses:

EEG data will be recorded using a 64-channel TMS-compatible electrode cap (Easy Cap)¹². Signals will be collected at 2000Hz (impedance: $<5k\Omega$, low-pass filter: 0.1-500Hz) during preand post-TMS stimulation epochs (-100ms to 200ms) (Figure 3). Fifty suprathreshold (120% AMT) TMS pulses will be applied to M1 while the subject is seated quietly with eyes open^{13,14}. This procedure will be conducted bilaterally at each assessment timepoint (Pre-PAS, Post-PAS 0', Post-PAS 30', Post-PAS 60'). Peripheral auditory and somatosensory stimulation effects will be minimized to avoid EEG artifact¹⁵. Data epochs (-1000 to 4000 ms with respect to TMS delivery) will be extracted for subsequent imaginary phase coherence analysis (IPC). Post-TMS coherence values between electrodes overlying M1 bilaterally (C3 and C4) will be calculated within the beta frequency range (15 to 30 Hz)¹⁶. These IPC values will be used to index local M1 excitability and connectivity with the contralateral homotopic region^{17,18}. Differences in single-channel evoked potentials in the TMS alone will be calculated to consider the effect of afferent peripheral input on TMS-elicited cortical responses.

Figure 2. Example of TMS-evoked EEG data recorded from stimulated (iM1) and non-stimulated (cM1) cortical regions.

Motor function assessment:

In the stroke group, arm function will be evaluated by the Wolf Motor Function Test (WMFT), shown to be a valid and reliable test of arm function in stroke¹⁹. In both groups, hand-held dynamometry will be used to measure grip strength and manual dexterity will be indexed by the Nine-hole Peg Test (9HPT)²⁰. These assessments will be carried out by a licensed physical therapist ([name]) prior to completing the PAS protocol. The serial reaction time task (SRTT) will be performed at each assessment time point to evaluate motor skill performance. The SRTT involves pressing a key that corresponds to a target square positioned on a screen in front of the participant as quickly and accurately as possible. The response time for repeated and random sequences will evaluate SRTT performance.

MRI acquisition: Scanning will be conducted at Emory University at the Center for Systems Imaging on a Siemens 3T Trio whole-body MRI scanner. A high-resolution T_1 scan (TR = 7.4ms, TE = 3.7ms, flip angle $\theta = 6^\circ$, FOV = 256mm, 160 slices, 1 mm thickness, scan time=3.2min) will be performed without contrast. The study team will have direct and immediate access to the data using Emory University's secure network server.

Statistical Plan:

To address the hypothesis that PAS induces LTP-like plasticity in both individuals with stroke and healthy controls, a three-way group (stroke, control) x condition (real PAS, sham PAS) x time (Pre-PAS, Post-PAS 0', Post-PAS 30', Post-PAS 60') analysis of variance (ANOVA) will be performed for the primary dependent measures (IPC and WMFT time). For the analysis, an alpha = .05 will be used and simple effects analyses will be performed for significant interaction effects.

Power analysis:

To ensure we have sufficient statistical power for our proposed aims, we used a combination of our standalone TMS data collected in participants with chronic stroke and TMS-EEG data collected to evaluate interhemispheric connectivity in young, healthy individuals¹⁶. To detect a hemispheric difference in iSP ratio of 0.06 with a common σ =0.11, b=0.8, a sample size of 27 subjects is required. In order to measure differences in TMS-evoked EEG responses in the hemisphere opposite the site of stimulation with a mean difference: 430µV.msec, common σ =288µV.msec, b=0.8, a sample size of 4 subjects is required. Due to the increased measurement variability in stroke, we chose a necessary sample size of n=30/group.

References:

Noninvasive brain stimulation to evaluate neural plasticity after stroke

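### Controls are individually matched to stroke participants, but the ANOVA carries no pair term or matching covariate; if matched participants are correlated on IPC, stroke-versus-control tests lose precision

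*Combined protocol and SAP*

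**What the plan says.** The Inclusion Criteria say that controls will be "matched for handedness, gender, age (within 5 years) and education (within 2 years) to each participant in the stroke group". The limits are set relative to each stroke participant, and 30 people are planned per group. The natural reading is therefore 30 one-to-one pairs, not groups balanced on average.

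The Statistical Plan opens with its purpose, "To address the hypothesis that PAS induces LTP-like plasticity in both individuals with stroke and healthy controls", and specifies "a three-way group (stroke, control) x condition (real PAS, sham PAS) x time" as the ANOVA for two primary measures, IPC and WMFT time. It adds that "an alpha = .05 will be used and simple effects analyses will be performed for significant interaction effects". Matching is not mentioned: there is no pair or block factor, no covariate for age, gender, handedness or education, and no statement of which factors are between or within participants.

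Under Motor function assessment, WMFT is assigned to the stroke group only. The Power analysis concerns a hemispheric difference and the response opposite the stimulated side. It contains no stroke-versus-control comparison.

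**The concern.** Individual matching is part of the design, and a group factor with no pair term would ordinarily be fitted as a between-subject factor on independent people. If age, gender, handedness or education influence the IPC quantity under test, the two members of a pair resemble each other, and the difference between group means varies less than the independent-groups error term assumes. The tests that contain group (main effect, group by condition, group by time and the three-way term) would then run below their nominal 5% level, with confidence intervals that are too wide.

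Two things would be at stake. A real stroke-control difference in IPC would be more likely to be missed, and a non-significant group interaction might be read as showing that both groups respond alike. Because simple-effects analyses follow only a significant interaction, a conservative interaction test also makes that follow-up less likely. The trial would have paid for matching on four variables without using the precision it may bring.

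**Working it through.** **The plan's own figures.** Inputs from the Power analysis: difference 0.06, SD 0.11; difference 430, SD 288 µV.msec; power 0.8 (read from b = 0.8); alpha 0.05, taken as two-sided. One-sample or paired normal formula: n = [SD × (1.960 + 0.842) / difference]².

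- (0.11 × 2.802 / 0.06)² = 26.4, rounded up to 27, as stated.
- (288 × 2.802 / 430)² = 3.52, rounded up to 4, as stated.

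An independent two-group formula would give 53 and 8 per arm, so the stated figures are not stroke-versus-control calculations. They take no credit for matching and do not change here.

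**Effect of leaving out the pairing.** Assume 30 complete pairs, one summary value per participant, common variance σ² and pair correlation r.

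- True variance of the difference in group means: 2σ²(1 − r)/30.
- Variance used by the unpaired analysis: 2σ²/30.
- The standard error is therefore overstated by the factor 1/√(1 − r). At r = 0.1 this is 1/√0.9 = 1.054; at 0.2, 1.118; at 0.3, 1.195; at 0.5, 1.414.

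Size and power come from 200,000 simulated trials at each r, comparing an unpaired t test (58 df) with a paired t test (29 df), both two-sided at 5%. Two standardised group differences are shown. The first, 0.545 = 0.06/0.11, is borrowed from the Power analysis for illustration only. The second, 0.736, gives the unpaired test 80% power at r = 0. The values of r are assumptions.

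| r | SE overstated by | Size, unpaired | Power at 0.545, unpaired v paired | Power at 0.736, unpaired v paired |
|---|---|---|---|---|
| 0 | 0% | 5.0% | 55% v 53% | 80% v 79% |
| 0.1 | 5% | 3.9% | 55% v 58% | 81% v 83% |
| 0.2 | 12% | 2.9% | 55% v 63% | 83% v 87% |
| 0.3 | 20% | 2.0% | 56% v 69% | 84% v 91% |
| 0.5 | 41% | 0.7% | 57% v 82% | 88% v 97% |

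The paired test holds about 5% at every r.

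For the 3-df group by condition by time test, take P[F(3,174) > critical value/(1 − r)], where 174 = 3 × 58. This assumes that everyone receives both conditions and that r is the same for all the change contrasts. The size is then about 3.4%, 2.1% and 1.1% at r = 0.1, 0.2 and 0.3.

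**Which r applies.** For the group main effect, r reflects how far the matching variables predict the level of IPC. For a change from Pre-PAS or a real-minus-sham change, stable person-level effects cancel, and r differs from zero only if those variables modify the response to PAS. The interaction terms may therefore sit near the top of the table.

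**The case against.** A reader might infer that the planned error term is simply wrong for every stroke-versus-control comparison. The documents do not support that, for four reasons.

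- The Statistical Plan never says that the groups are independent. That is the ordinary reading of a silent text.
- The error term is wrong only if r is non-zero for the contrast analysed. No value of r is given, and at r = 0 the planned analysis is correct and pairing costs a little power.
- WMFT time has no control values, so there is nothing to pair.
- For within-person change, nothing in the documents shows that age, gender, handedness or education modify the PAS response, so the larger losses in the table are unsupported there.

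A reader might also infer a risk of false positives. With positive correlation the error runs the other way: the tests are conservative and the estimated difference is not biased. Matching still makes the groups comparable on the four variables, with or without a pair term.

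Finally, the stated hypothesis is that PAS works in both groups. That is chiefly a condition-by-time question, and the error terms of the tests within each group do not depend on the pairing.

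All of this stands, and it limits the point to efficiency in the IPC group contrasts. It does not remove the gap: the plan sets up individual matching, puts group in the primary ANOVA, and does not say whether the matching is used. The risk is also uneven. Pairing costs about one point of power if r = 0 and gains several points at modest positive r.

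**Conclusion.** The point holds as a cheap improvement. The matching under Inclusion Criteria does not reach the Statistical Plan. If r is positive for the IPC contrast analysed, the standard error of a stroke-control difference is overstated by 5%, 12% and 20% at r = 0.1, 0.2 and 0.3. At a standardised difference of 0.545, the power forgone is about 3, 7 and 13 points; at 0.736 it is about 2, 4 and 7.

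These figures assume 30 complete one-to-one pairs, one summary value per participant and a two-sided 5% test. The actual loss cannot be derived from the documents, because r is not given and may be near zero for within-person change. WMFT time, the within-group PAS tests and the stated sample sizes of 27 and 4 are unaffected.

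**What to change.** Add to the Statistical Plan, for stroke-control comparisons of IPC only:

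- **Summary value.** Reduce each participant to one number: the real-minus-sham change if each participant receives both conditions, otherwise the change from Pre-PAS. The paragraph on PAS protocols leaves this unclear, since it assigns one intervention per session and then speaks of a PAS group. If conditions differ between people, use pairs only where both members received the same condition.
- **Analysis.** Take stroke minus control within each pair and report the mean difference with a 95% CI (29 df with 30 complete pairs). Alternatively, adjust for age, gender, handedness and education.
- **Incomplete pairs.** State how they are handled. If a mixed model is used to keep them, include random effects for participant and participant by condition, as well as pair, pair by condition, pair by time and pair by condition by time. The participant-by-condition effect matters. In simulations with 30 pairs, both conditions, four times, r = 0 and residual variance 1, a model without it (and without the pair-by-condition-by-time effect) rejected a true null for group by condition about 9%, 14% and 20% of the time. The assumed participant-by-condition variances were 0.1, 0.25 and 0.5. Without pair by condition by time, the three-way term does not benefit from the pairing.

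Leave the within-group PAS tests as they are.

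The cost is one or two sentences and a pair identifier in the dataset, with no new participants or measurements. The downside is a fall in error df for the group contrast from 58 to 29, worth about one percentage point of power if matching induces no correlation.

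### The plan leaves PAS condition undefined as within or between participants, does not randomise condition or order, and fits no session term, so real versus sham can be confounded for IPC.

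*Combined protocol and SAP*

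**What the plan says.** All references are to the combined protocol and SAP.

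- **PAS section, assignment of condition:** "For each PAS session, individuals will either receive traditional PAS, ccPAS or a sham stimulation intervention". This ties condition to the session.
- **PAS section, next sentence:** "Regardless of PAS group, each participant will receive 180 paired stimuli". This ties condition to a group of participants. The same paragraph later speaks of a PAS condition.
- **Research Plan, visits:** "Up to 5 testing sessions will be performed". No minimum number of sessions, spacing or washout is given.
- **Statistical Plan:** a three-way ANOVA of group by "condition (real PAS, sham PAS) x time". Time means the four assessments around one PAS application (Pre-PAS and 0, 30 and 60 minutes after). The primary measures are IPC and Wolf Motor Function Test (WMFT) time.
- **Motor function assessment:** "The response time for repeated and random sequences will evaluate SRTT performance". In the plan's own text this is the only use of the word random, and it describes task stimuli, not assignment.

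No section describes randomisation, counterbalancing, a sequence or a session term, or says whether ccPAS is pooled into real PAS.

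**The concern.** Real versus sham is the contrast that tests whether PAS induces LTP-like plasticity. A sham condition protects that contrast only if chance or balance decides who receives it, or where it falls in the sequence of sessions.

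The two readings of the text lead to different problems.

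- **Several PAS sessions per participant:** if real sessions tend to fall earlier or later than sham sessions, any change in response across sessions is read as an effect of stimulation.
- **One PAS session per participant:** order does not arise, but the real and sham participants may differ for reasons other than stimulation.

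The readings also call for different error terms, so the ANOVA is not fully specified until the design is stated.

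**Working it through.** **The plan's own figures.** The Power analysis gives 27 and 4 subjects. Both reproduce as a two-sided 0.05, 80% power, one-sample or paired normal calculation, n = (SD × (1.960 + 0.842) / difference)²:

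- iSP ratio: (0.11 × 2.802 / 0.06)² = 26.4, rounded up to 27.
- Evoked EEG response: (288 × 2.802 / 430)² = 3.5, rounded up to 4.

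Neither calculation concerns real versus sham, and neither has an order or session component.

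**What the Pre-PAS value removes.** Suppose a session adds the same amount to all four time points. That amount cancels in the condition by time interaction, although it stays in the condition main effect. If instead the change from Pre-PAS to post-PAS itself drifts between sessions, through habituation or a residue from the previous session, nothing cancels.

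**Size of the bias, within-participant reading.** Inputs:

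- d, the drift in within-session change between the earlier and the later session, in SDs of the paired real-minus-sham difference. Assumed 0.2 to 0.3; the documents give none.
- f, the share of participants receiving real first. Assumed 1, 0.8 or 0.65; the documents give none.
- n = 60 (both groups of 30, same drift in each) or n = 30 (one group).
- True effect zero, two-sided alpha 0.05 (the plan gives .05 without sidedness).

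Bias = f × d − (1 − f) × d = d × (2f − 1). The rejection probability comes from the noncentral t distribution with n − 1 degrees of freedom and noncentrality bias × √n. For example, d = 0.3, f = 1 and n = 60 give 0.3 × 7.746 = 2.32 and a rejection probability of 0.628.

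| f | d | Bias (SD) | n = 60 | n = 30 |
|---|---|---|---|---|
| 1 | 0.2 | 0.20 | 33.2% | 18.5% |
| 1 | 0.3 | 0.30 | 62.8% | 35.5% |
| 0.8 | 0.2 | 0.12 | 15.0% | 9.7% |
| 0.8 | 0.3 | 0.18 | 27.9% | 15.9% |
| 0.65 | 0.2 | 0.06 | 7.4% | 6.2% |
| 0.65 | 0.3 | 0.09 | 10.5% | 7.6% |

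Mixed orders also add variance to the observed differences. A simulation at n = 60 that includes it gives slightly lower rates when order is only partly unbalanced: 14% and 26% at f = 0.8, 7% and 9% at f = 0.65.

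**Effect of balancing.** At f = 0.5 the bias is zero. In simulation at n = 30 with d = 0.2 and 0.3, a balanced order without a session term rejects 4.7% and 3.9% of the time, which is slightly conservative; with a session term the rate is about 5%. If everyone has the same order, condition and session coincide and no session term can be fitted.

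**Carry-over.** Take all six orders of PAS, ccPAS and sham in equal numbers, with session and participant effects fitted. Let PAS alone leave a residue c in the next session. Least squares then gives a PAS-minus-sham estimate biased by −c/3, because sham sometimes follows PAS but PAS never follows itself. Balanced order deals with drift, not with this.

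**The case against.** The plan is silent on order; it does not state a fixed one. A reader might infer from the 63% figure that the trial runs real stimulation first. No section says so, and that figure is a worst case built on two assumptions. It also treats the analysis as a single paired comparison, whereas the plan has a four-level time factor and two groups, and it supposes that all 60 participants complete both conditions.

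A reader might also infer that learning on the serial reaction time task (SRTT) contaminates the primary result. The documents do not support that. SRTT is not a primary measure and is in no stated model, and nothing says that one repeated sequence is reused across sessions. WMFT is described only before the PAS protocol is completed, so no post-PAS WMFT change is described for drift to distort; that mismatch with the four-time-point model is a separate matter. The point therefore rests on IPC, recorded while the participant sits quietly, where task practice is a weak mechanism and habituation or carry-over more plausible ones.

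The protocol describes the induced changes as transient, which argues against large carry-over if sessions are well separated. The separation is not stated.

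If each participant has one PAS session, order and carry-over do not arise and no session term is needed. This changes the form of the problem without removing it, since allocation would still be unrandomised.

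All these limits on size and mechanism stand. None supplies the missing design statement or assignment method.

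**Conclusion.** The point holds as a gap in design and model. The documents leave condition undefined as within or between participants, give no random or balanced assignment, and fit no session term, so the real-versus-sham contrast for IPC can be confounded under either reading.

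The documents do not show that it is confounded, or by how much. Under the assumed drifts, the false-positive rate runs from near nominal (about 6% at n=30, mild imbalance, smaller drift) to 63% (n=60, real always first, larger drift). These are illustrations under the within-participant reading and do not measure the allocation problem in a parallel design.

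A reader might infer that balancing order and adding a session term leaves no bias at all. That is true for session drift but not for unequal carry-over. The sponsor should make the change, because a fixed order cannot be repaired in the analysis.

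**What to change.** 1. State whether condition is within or between participants, and how ccPAS enters the two-level real or sham factor.
2. If within, randomise each participant to a balanced order of the conditions that participant will receive, separately in the stroke and control groups. Fit session number as a fixed effect and participant as a random effect. Because the drift of concern is in the within-session change, let session interact with time, or analyse change from Pre-PAS.
3. If between, randomise allocation within each group.
4. State the interval between sessions. Check carry-over with a preceding-condition term as a sensitivity analysis. With only two conditions per participant that term is weakly estimable, so the stated interval is then the main protection.
5. If SRTT is compared across sessions, rotate the repeated sequences across conditions.
6. If sessions are already complete, report the order used and fit the session term where orders varied.

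The cost is an order or allocation list, a few model degrees of freedom and some scheduling constraint. The plan does not say that every participant receives all three conditions, and the fix should not require it if that would add visits.

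### IPC is a C3–C4 coherence, yet the plan also reads it as local M1 excitability; a change in one IPC value cannot be attributed to local M1, and no single-channel M1 response is assigned to the PAS test

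*Combined protocol and SAP*

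**What the plan says.** All references are to the combined protocol and SAP.

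- **EEG recording of TMS-evoked cortical responses.** IPC is defined on an electrode pair: "Post-TMS coherence values between electrodes overlying M1 bilaterally (C3 and C4) will be calculated", in the 15 to 30 Hz band. Two meanings are then attached to it: "These IPC values will be used to index local M1 excitability and connectivity with the contralateral homotopic region". Both hemispheres are stimulated: "This procedure will be conducted bilaterally at each assessment timepoint". That gives up to two IPC values per time point, one per stimulated side, each for the same pair.
- **Same section, single-channel data.** Differences in "single-channel evoked potentials in the TMS alone will be calculated to consider the effect of afferent peripheral input on TMS-elicited cortical responses". No other purpose is given for them.
- **Figure 2 caption.** "Example of TMS-evoked EEG data recorded from stimulated (iM1) and non-stimulated (cM1) cortical regions". The signal at the stimulated M1 is therefore already recorded.
- **Paired associative stimulation.** Traditional PAS pairs median nerve stimuli with "TMS delivery over the ipsilesional (stroke) or non-dominant (control) cortex", so it acts on one named side. The section says that traditional PAS excites M1 and that ccPAS produces local LTP-like effects.
- **Statistical Plan.** The group × condition × time ANOVA is introduced with "To address the hypothesis that PAS induces LTP-like plasticity in both individuals with stroke and healthy controls". Its primary measures are IPC and WMFT time. No single-channel response appears in it.

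**The concern.** One between-site number is given two interpretations. If IPC rises after real PAS and not after sham, the EEG section as written would let the investigators report greater M1 excitability. The same rise could reflect a change in the opposite hemisphere or in the connection between the two. A null result could also hide offsetting changes.

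This matters because the protocol describes the intervention largely in terms of motor cortex excitability, while the only planned single-channel analysis answers a different question. Using those potentials later to support an excitability claim would be post hoc: no electrode, metric, window or side is fixed for that purpose.

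**Working it through.** **The plan's own figures.** There is none for IPC: no effect size, SD or formula. The two sample sizes under Power analysis do reproduce with n = ((1.960 + 0.842) × SD/difference)², taking the SD as that of a within-subject difference and alpha as two-sided (both assumed):

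- iSP ratio: (2.802 × 0.11/0.06)² = 26.4, so 27.
- Evoked response opposite the stimulated side: (2.802 × 288/430)² = 3.5, so 4.

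They are not in dispute. Neither concerns IPC or the response at the stimulated M1.

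**Assumed two-channel model.** The documents supply only the electrode pair; everything else here is an assumption.

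- C3 = a·S + √L·U + √n3·N3
- C4 = c·S·exp(−iφ) + √n4·N4
- S, U, N3 and N4 are independent with unit power.
- Imaginary coherence = a·c·sin φ / √[(a² + L + n3)(c² + n4)]

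Baseline is a = c = n3 = n4 = 1, L = 0, φ = 60°.

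| Change | Calculation | Result | Against baseline |
|---|---|---|---|
| Baseline | 0.866/√(2×2) | 0.433 | – |
| C3 response doubled, addition unrelated to the existing signal (L = 3) | 0.866/√(5×2) | 0.274 | −37% |
| C3 response doubled, phase-locked, C4 unchanged (a = 2) | 0.866×2/√(5×2) | 0.548 | +26% |
| Both responses doubled (a = c = 2) | 0.866×4/5 | 0.693 | +60% |
| Only C4 response doubled (c = 2) | 0.866×2/√(2×5) | 0.548 | +26% |
| C4 background power doubled (n4 = 2) | 0.866/√(2×3) | 0.354 | −18% |
| Lag 30° instead of 60° | 0.5/2 | 0.250 | −42% |

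The third and fifth rows are identical although the change is on opposite sides. The second and third are both C3 increases and move in opposite directions.

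**Sensitivity.** With response-to-background power varied from 0.25 to 4 (n3 = n4 = 1/ratio, n4 doubled in the background case), the first four changes run −21% to −46%, +58% to +8%, +150% to +18% and +58% to +8%. The C4 background case runs −25% to −9%, and the lag case stays at −42%. A phase-only version, obtained by simulation, gives about 0.35 at baseline and then 0.22, 0.46, 0.60, 0.46, 0.28 and 0.20: the same pattern.

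**Second parameterisation.** Let g be the local gain at C3 and c the coupling that carries it to C4, with unit background and a 60° lag. IPC = 0.866·c·g²/√[(g² + 1)(c²g² + 1)].

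- g = 1, c = 0.5: 0.433/√(2×1.25) = 0.274.
- g = 1.5, c = 0.5: 0.974/√(3.25×1.5625) = 0.432.
- g = 1, c = 1: 0.866/2 = 0.433.

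A purely local change and a purely coupling change give practically the same IPC. Power at C3 tells them apart: g² + 1 = 3.25 against 2.00.

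**The case against.** **The protocol says index, not separate.** The Statistical Plan speaks of LTP-like plasticity without the word local, and the model itself shows IPC moving when the local response changes. This stands in part. A reader might infer that IPC carries no local information or is unfit as a plasticity measure. The documents do not support that: IPC bears on plasticity, especially under ccPAS, and it can support a connectivity conclusion. What fails is attributing a change in IPC to local M1.

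**Both sides are stimulated.** A reader might infer that IPC can never show which side changed. That does not follow. Suppose a doubled gain at one M1 amplifies both its own response and input arriving from the other side. Listing the value when stimulating the ipsilesional side first and the other side second:

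- ipsilesional gain doubled: 0.693 and 0.548
- opposite gain doubled: 0.548 and 0.693
- coupling doubled in both directions: 0.548 and 0.548

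The pairs differ. However, coupling changes that differ by direction could blur them, and the Statistical Plan neither says how the two values enter the ANOVA nor prespecifies such a comparison. The point is therefore limited to a single IPC value.

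**Sources cited for the sentence (references 17 and 18) may justify the local reading.** They were not available, and no IPC formula is given. So the local reading is not supported by the protocol's definition alone; a reader should not take it as refuted outright.

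**A single-channel analysis bearing on excitability is already planned.** True: the protocol describes afferent inhibition as reduced cortical excitability. What is missing is the link from a single-channel response to PAS condition and time.

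**This is a pilot, and the figures are assumed.** Both are true. They limit the severity and make the model an illustration, not an estimate of an expected effect.

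**Conclusion.** The concern holds in this limited form. On the definition given in the EEG section, a change in one IPC value cannot be attributed to local M1 excitability rather than to the opposite hemisphere or the coupling, and no planned single-channel response is assigned to the PAS-by-time test.

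No size can be given for this trial. Direction and amount depend on the lag, the signal-to-background ratio and the kind of local change, none of which the documents settle. The conclusion rests on IPC being computed from the C3–C4 pair as stated, not on the illustrative values.

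The primary test can still be run and interpreted as interhemispheric connectivity, so this is a correction that should be made and not a defect that invalidates the primary analysis.

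**What to change.** 1. **EEG section:** delete local M1 excitability from what IPC indexes, and interpret IPC as interhemispheric connectivity.
2. **Statistical Plan:** prespecify, as a secondary measure outside the primary alpha, the single-channel TMS-evoked response at the electrode over the PAS-targeted M1 when that M1 is stimulated. Fix one metric and one window. An example is the rectified area under the evoked response, in the µV.msec unit that Power analysis already uses, over a single post-artifact window within 0–200 ms. Use the same group × condition × time model. The protocol names the side only for traditional PAS, so also state which side is analysed for ccPAS and sham.
3. **Interpretation:** state that local-excitability claims will not be based on IPC alone.

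**Cost:** text changes in two sections and one more outcome to process and report. No new recording is needed, and the primary measures, primary alpha and sample size are unchanged.

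**Downsides:** the pulse artifact near the coil must be handled. A trial-averaged response detects only phase-locked change, so it should not be the sole basis for every local claim either. Precision is unknown, because the only evoked-response SD given (288 µV.msec) is for the hemisphere opposite the stimulation.
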